CDM	Clinical Data Management
CI	confidence interval
CNS	central nervous system
CR	complete response
CSR	Clinical Study Report
CT	computer tomography
CTCAE	Common Terminology Criteria for Adverse Events
DLBCL	diffuse large B-cell lymphoma
DLT	dose limiting toxicity
DRE	disease-related events
DRT	data review team
eCRF	electronic case report form
ECG	electrocardiogram
ECOG	Eastern Cooperative Oncology Group
EOI	Events of interest
GCB	germinal center B
GI	Gastrointestinal
GSO-DM	Global Study Operations-Data Management
Ig	Immunoglobulin
IP	investigational product

Abbreviation or Term	Definition/Explanation
IPD	important protocol deviation
IPI/aalPI	international prognostic index/age-adjusted international prognostic index
IV	intravenous
KM	Kaplan-Meier
LDH	lactate dehydrogenase
MedDRA	Medical Dictionary for Regulatory Activities
MRD	minimal residual disease
ND	not done
NGS	next generation sequencing
OS	overall survival
PET-CT	positron emission tomography - computed tomography
PFS	progression free survival
QTc interval	QT interval corrected for heart rate using accepted methodology
SAP	statistical analysis plan
SAS	statistical analysis software
TFLSD	table figure listing shell document

1. Introduction

The purpose of this Statistical Analysis Plan (SAP) is to provide details of the statistical analyses that have been outlined within the protocol amendment 3 for study 20150291, Blinatumomab dated 18 July 2018. The scope of this plan includes the primary analysis and the final analysis that are planned and will be executed by the Amgen Global Biostatistical Science department unless otherwise specified.

2. Objectives, Endpoints and Hypotheses

2.1 Objectives and Endpoints

Objectives	Endpoints
Primary	

 To determine minimal residual disease (MRD) negative rate following blinatumomab treatment in high-risk Diffuse Large B-cell Lymphoma (DLBCL) subjects who are MRD-positive post-autologous hematopoietic stem cell transplantation (aHSCT). 	
 MRD negativity in cycle 1 of blinatumomab, defined as the best MRD response on day 57 or day71(+3 days) via MRD testing
Secondary	

 To describe the efficacy of blinatumomab in relation to progression-free survival (PFS), duration of MRD-negative status, and overall survival (OS) 	
 PFS Duration of MRD negative status OS

 To evaluate the safety and tolerability of blinatumomab 	
 Incidence, grade and severity of treatment emergent adverse events (AE)
Exploratory	

 To describe the incidence of anti-blinatumomab antibody 	
 Incidence of anti-blinatumomab antibody formation

 To describe the MRD-negative rate over time following blinatumomab treatment 	
 MRD negative rate calculated at each time point measured following blinatumomab treatment

 To describe rate, features and outcomes of allogeneic hematopoietic stem cell transplantation (alloHSCT) following treatment with blinatumomab 	
 Incidence of alloHSCT (rate and number of subjects with alloHSCT) and the feature and clinical outcomes

Objectives	Endpoints
Exploratory (Continued)	

 To describe the relationship between clinical and baseline parameters and response to blinatumomab treatment 	
 Relationship between pre-specified co-variables with MRD negative status and clinical outcomes

 To describe MRD status relative to clinical relapse 	
 Relationship between MRD negative status and clinical relapse

 To describe MRD status prior to treatment with blinatumomab in positron emission tomography (PET)-computed tomography (CT) negative high-risk DLBCL subjects following aHSCT: 
 - To describe MRD-positive status post aHSCT - To describe the rate and timing of MRD-negative to MRD-positive change at screening and during the run-in period 	
 Summary of MRD characteristics prior to treatment with blinatumomab: 
 - The percentage of MRD positivity in PET-CT negative subjects post aHSCT - Rate and timing of MRD negative to MRD positive change during the 24-month run-in period

2.2 Hypotheses and/or Estimations

The study will estimate the MRD-negative response rate after treatment with blinatumomab in subjects with high-risk DLBCL who are MRD-positive following aHSCT.

The clinical hypothesis is that the MRD negative response rate will be greater than 10%. Achieving an MRD negative response rate of 30% would be of scientific and clinical interest.

No formal statistical hypothesis will be tested. The study will estimate the MRD negative rate and also calculate its 95% exact binomial confidence interval.

3. Study Overview

3.1 Study Design

This is a phase 2, multicenter, open-label, single arm estimation study in adult subjects with high-risk DLBCL that are PET-CT negative post aHSCT. The study will consist of the following periods:

- Screening period (up to 28 days)
- Run-in period of up to 24 months to evaluate MRD status and assess eligibility for treatment assignment
- Treatment period of 12 weeks (which includes 8 weeks of treatment with blinatumomab followed by a 4-week treatment-free period)
- Safety follow-up visit 30 days after the last dose of blinatumomab
- Long-term follow-up period that begins after the safety follow-up visit is completed until 1 year from the first dose of blinatumomab.

The study will enroll approximately 90 subjects in the study with relapsed/refractory, biopsy-proven, high-risk DLBCL who are PET-CT negative at 90 days (\pm 30 days) post aHSCT (see Section 4.1 Part 1 Inclusion and Exclusion criteria of the protocol amendment 3 dated 18 July 2018).

During the run-in period, subjects will be followed by clinic visits at 3, 5, 7, and 9 months, and thereafter every 3 months (\pm 1 week) up to 24 months for monitoring of MRD status in plasma by next generation sequencing (NGS)-based assay. Subjects who remain MRD-negative by the end of the 24-month run-in period will end the study. It is expected that approximately 30 subjects will be MRD-positive either at screening or become MRD-positive during the 24-month run-in period.

The number of subjects enrolled may be altered in order to ensure that approximately 30 subjects are assigned to treatment with blinatumomab. Enrollment may be stopped once approximately 30 subjects have been assigned to treatment with blinatumomab. Subjects, who are MRD-positive at enrollment or become MRD-positive during the run-in period, and who meet all other part 2 eligibility criteria (see Section 4.2 Part 2 Inclusion and Exclusion criteria of the protocol amendment 3 dated 18 July 2018), will be assigned to treatment with blinatumomab.

Blinatumomab will be administered as a continuous intravenous (IV) infusion. Cycle 1 will be 12 weeks (84 days) in duration, which includes 8 weeks (56 days) of blinatumomab IV infusion followed by a 4-week (28 days) treatment-free interval.

Blinatumomab will be dosed at 9 µg/day for 7 days, followed by 28 µg/day for 7 days and 112 µg/day for 42 days.

[figure not shown]
MRD status will be assessed at cycle 1 day 1 prior to blinatumomab infusion, on cycle 1 days 15 and 43, the end of the blinatumomab infusion (day 57) and 2 weeks after the end of the blinatumomab infusion (day 71 + 3 days) to evaluate disease status. A PET-CT will be performed only if a subject remains MRD-positive (day 57 of cycle 1 assessment) after blinatumomab or has clinical signs and symptoms of disease progression.

A safety follow-up visit will occur 30 days (+ 3 days) after the last dose of blinatumomab for assessment of disease-related events, adverse events, and serious adverse events. A long-term follow-up period to assess disease status and OS begins at completion of the safety follow-up visit and continues for 1 year from the first dose of blinatumomab. Subjects will be followed via clinic visit every 3 months (\pm 2 weeks) for MRD assessment and by institutional standard of care disease evaluation (PET-CT or CT) until relapse at which time the subject will be followed for survival via telephone contact.

A Data Review Team (DRT) will monitor the study for safety on a regular basis.

The overall study design is described by a study schema below.

Study Design and Treatment Schema

EOS = end of study; IP = investigational product;; MRD = minimal residual disease; PET-CT = positron emission tomography/computed tomography

^a Run-in period is up to 24 months in duration. During the run-in period, enrolled subjects that are MRD negative/PET-CT negative will be followed at 3, 5, 7 and 9 months and thereafter every 3 months up to 24 months for monitoring of MRD status by next generation sequencing.

^b At any time after enrollment and during the run-in period subjects who turn MRD positive/ PET-CT negative and that meet all other part 2 eligibility will be assigned to treatment with blinatumomab. Subjects that do not display MRD positivity at the end of the 24-month run-in period will end the study.

^c MRD status will be assessed at cycle 1 day 1 prior to blinatumomab infusion, on cycle 1 days 15 and 43, the end of the blinatumomab infusion (day 57), and 2 weeks after the end of the blinatumomab infusion (day 71 + 3 days).

^d Long-term follow-up period will be 1 year from the first dose of blinatumomab. Subjects will be followed via clinic visit every 3 months (± 2 weeks) until relapse and from this point onwards via telephone contact for overall survival.

3.2 Sample Size

This is a single-arm estimation study. It is anticipated that an MRD negative rate of 10% could be observed by chance in this study. Therefore, if the observed rate of MRD negativity is at least 30%, then the sample size for this study ($N = 30$) is sufficient to demonstrate that, with 95% confidence, the rate of achieving MRD negativity is greater than 10%. This would also be sufficient to demonstrate evidence of clinical activity.

A table showing the exact binomial confidence intervals for different observed rates of MRD negativity with a sample size of $N = 30$ is presented below:

Table 3-1. Confidence Intervals for Different Observed Rates of MRD Negativity With a Sample Size of 30

Observed rate of MRD negativity, n (%)	Lower 95% Confidence Limit (%)	Upper 95% Confidence Limit (%)
8 (26.7)	12.3	45.9
9 (30.0)	14.7	49.4
11 (36.7)	19.9	56.1
12 (40.0)	22.7	59.4
14 (46.7)	28.3	65.7

The study will enroll approximately 90 subjects to achieve the desired sample size of 30 subjects who are MRD positive at the time of enrollment or during the run-in period. As part of the run-in period, subjects will be followed by clinic visits at 3, 5, 7, 9 and 12 months and thereafter every 3 months up to 24 months for monitoring of MRD status, thus it could be more than 30 subjects who at some point become MRD positive before the study ends. Any subject who becomes MRD positive after the first 30 subjects with treatment of blinatumomab will still be eligible for treatment and included in Full Analysis Set. Therefore the final sample size may be higher than 30 subjects.

3.3 Adaptive Design

Not Applicable

4. Covariates and Subgroups

4.1 Planned Covariates

The relationship of clinical and baseline covariates to endpoints will be explored, if appropriate. Clinical and baseline covariates include:

- Age at enrollment (<65, 65-74, 75-84, ≥85 years)
- Sex (Male vs. Female)
- Race (categories will depend on the data)
- Stage at diagnosis (I, II, III, IV. Categories maybe combined depending on the data)
- International prognosis index (IPI) at diagnosis and secondary IPI at relapse (Low (0-1), Low – intermediate (2), High – intermediate (3), High (4-5))
- Age-adjusted IPI (aaIPI) at diagnosis and secondary aaIPI at relapse (Low (0), Low - intermediate (1), High – intermediate (2), High (3))
- Cell of origin (if available locally) (GCB, Non-GCB/ABC)
- Double hit (Yes, No, Not Done)

- Triple hit (if available locally) (Yes, No)
- Refractory to frontline treatment (Yes, No)
- Relapse within 1 year of diagnosis (Yes, No)
- High-risk first complete remission (Yes, No)
- MRD-positive at enrollment/MRD-positive within 6 months from enrollment/MRD-positive any time later during run-in.

4.2 Subgroups

Analysis of primary and secondary endpoints in the subgroups defined by the above baseline covariates will be explored, if appropriate, depending on the sample size.

5. Definitions

Age-adjusted international prognostic index (aalPI)

aalPI score will be derived by assigning one point to each of the risk factors: disease stage III/IV, elevated LDH level and ECOG score ≥ 2 (please refer to Appendix D of the protocol).

Age at enrollment

Subject age at enrollment will be collected in years in the clinical database.

Baseline

Unless otherwise specified the baseline value for parameters/assessments scheduled to be performed on the same day as the first administration of blinatumomab, is the last value measured before the first administration of blinatumomab on that day. For parameters/assessments not scheduled to be performed (or scheduled but not performed) on the same day as the first administration of blinatumomab, the baseline value is the value measured closest to the day of first administration of blinatumomab.

Cumulative dose of investigational product (blinatumomab)

The cumulative dose in μg is defined as the following with summation over infusions:

\sum (duration of infusion [days] for each dose received x dose received [μg]). Cumulative dose will be calculated within blinatumomab cycle 1.

Death date

For subjects who die during the study, the death date will be recorded on the event, end of study and/or survival status eCRF. The earliest death date will be used for analysis if the dates are inconsistent among these CRF pages. For deaths collected after a subject has ended study (eg, through public records), the death date will be recorded on the long-term follow-up.

Duration of blinatumomab treatment

For each infusion episode within cycle 1, the duration of exposure to blinatumomab will be calculated by subtracting the start date and time from the stop date and time. If either a start or stop time is missing, only the date portion will be used in calculating the duration of a specific infusion. The duration will be the sum of the individual infusion durations within cycle 1. The duration will be rounded to the nearest day.

Duration of MRD-negative status

The duration of MRD-negative status will be assessed only in subjects who achieve MRD-negative status after blinatumomab treatment. Subjects missing post-baseline MRD assessments will be considered not to have achieved MRD negative status.

Duration of MRD-negative status will be defined from the time when a negative MRD result is first established until documented MRD-positive reoccurrence, or disease progression (or, death due to any cause). Subjects without any of these events at the time of the analysis will be censored at their last disease assessment date.

End of Treatment

End of Treatment is defined as the last assessment for the protocol-specified treatment phase of the study for an individual subject.

End of follow-up

End of Follow-up is defined as when the last subject completes the last protocol-specified assessment in the study.

End of study

For a subject: End of study for a subject is defined as the last day that protocol-specified procedures are conducted for an individual subject.

For the study as a whole: The end of trial is defined as the date when the last subject is assessed or receives an intervention for evaluation in the study (ie, last subject last visit), following any additional parts in the study (eg, long-term follow-up), as applicable.

The primary completion date: The primary completion date is defined as the date when the last subject is assessed or receives an intervention for the final collection of data for the primary endpoint, for the purposes of conducting the primary analysis, whether the study concluded as planned in the protocol or was terminated early.

High-risk first complete remission

High-risk first complete remission is defined as subjects who an interim PET-CT positive or less than complete remission to frontline chemotherapy AND achieved complete remission to platinum-containing salvage)

as collected on the Prior Anti-Cancer Therapies for Current Malignancies eCRF page.

International prognostic index (IPI)

International prognostic index (IPI) at diagnosis will be collected on the 'IPI at diagnosis' field on the DLBCL Disease History (Staging and Risk Initial) eCRF page. Secondary IPI at relapse will be collected on the 'IPI prior to S1' field on the DLBCL Disease History (Staging and Risk Prior S1) eCRF page.

Minimum residual disease (MRD)

Minimum residual disease (MRD) is defined as negative when the tumor clone sequence in plasma is below the assay limit of detection (to be determined in the assay validation). Positive MRD status will be defined as plasma levels above the assay limit of detection. All subjects in the treatment period are considered MRD positive, regardless whether the Cycle 1 Day 1 MRD test results are positive or negative because these subjects have been tested MRD positive in the run-in period.

Overall survival (OS)

Overall survival will be defined from the first dose of blinatumomab treatment until death due to any cause. Subjects still alive at the time of the analysis will be censored at date last known to be alive.

Percent of intended dose of blinatumomab

For cycle 1, the percent of intended dose of blinatumomab will be the cumulative dose divided by the planned cumulative dose. The planned cumulative dose for cycle 1 will be $(9 \mu\text{g} \times 7 \text{ days}) + (28 \mu\text{g} \times 7 \text{ days}) + (112 \mu\text{g} \times 42 \text{ days}) = 4963 \mu\text{g}$.

Progression free survival (PFS)

Progression free survival (PFS) is calculated as the time from the date of first dose of blinatumomab until the date of diagnosis of relapse of lymphoma (by PET-CT, CT, clinical assessment or relapse biopsy, whichever is the preferred method), or date of death, whichever is the earliest. Subjects alive who did not have progression will be censored at last date of tumor assessment.

Refractory to frontline treatment

Refractory to frontline treatment is defined as failure to achieve complete response as the best response after completion of frontline chemotherapy, as collected on the Prior Anti-Cancer Therapies for Current Malignancies eCRF page.

Relapse within 1 year of diagnosis

A subject will be classified as relapsed within 1 year of diagnosis if the difference between the earliest date of relapse captured on the History of Relapses eCRF page and date of diagnosis on DLBCL Medical History eCRF page is less than 1 year.

Date of first relapse – Date of diagnosis + 1 < 365.25

Stage at diagnosis

As collected on the 'Ann-Arbor' field on the DLBCL Disease History (Staging and Risk Initial) eCRF page.

Study day 1

Study day 1 is defined as the first day that protocol-specified investigational products are administered to the subject.

Study day

Pre study day 1: study day= (date – date of Study Day 1)

On and after study day 1: study day= (date - date of Study Day 1) + 1

Treatment-emergent adverse event (TEAE)

Adverse events (AEs) starting on or after first dose of protocol-specified therapy as determined by the flag indicating if the adverse event started prior to the first dose on the Adverse Events Summary CRF and up to and including 30 days after the end of protocol-specified therapy. This reporting window also applies to treatment-emergent serious adverse events (SAEs).

Treatment-emergent disease-related event

Events categorized as Disease-related Events (DREs) starting on or after first dose of blinatumomab as determined by the flag indicating if the event started prior to the first dose on the Events CRF and up to and including 30 days after the end of blinatumomab.

Disease Related Events

Subject incidence of disease related events and fatal disease related events in the blinatumomab treatment period (through the safety follow-up visit) will be tabulated by

system organ class and preferred term. Refer Protocol section 9.1.1 for more details on disease related events by their system organ class.

Triple hit

Triple hit is defined as the positive rearrangement of c-MYC, BCL2 and BCL6 as collected on the 'Disease-Specific Features on the DLBCL Disease History (COO)' eCRF page.

6. Analysis Sets

This study will define the following analysis sets for the purpose of statistical analysis: Full Analysis set, Primary analysis Set, Target Dose Analysis Set, Pre-treatment Analysis Set and Dose Limiting Toxicity (DLT) Analysis Set.

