7.2.3 Run-in Period

Once a subject is enrolled (ie, subject has met the Part 1 eligibility criteria) he/she will enter the run-in period.

During the run-in period subjects who are MRD-negative/PET-CT negative will complete MRD monitoring visits (run-in visit 1) at 3, 5, 7, and 9 months, and thereafter every 3 months (\pm 1 week) for up to 24 months (see Schedule of Assessments [Table 4](#)).

Subjects who remain MRD-negative by the end of the 24-month run-in period will end the study. Subjects who are MRD-positive at enrollment or become MRD-positive at any time during the run-in period will complete run-in 2 visit (treatment assignment visit).

MRD-positive subjects that meet all other part 2 eligibility criteria (see [Section 4.2](#)) will be assigned to treatment with blinatumomab. Subjects who do not meet Part 2 eligibility criteria will end the study.

In order to confirm part 2 eligibility and treatment assignment, all procedures during run-in visit 2 (see [Table 4](#)) should be initiated immediately after confirmation of MRD positivity (except as noted below), and completed within 7 days from the first dose of blinatumomab (day 1, cycle 1). A PET-CT must be performed at the run-in 2 visit in subjects that become MRD-positive during run-in 1. Subjects that are MRD-positive at screening may qualify for treatment assignment to blinatumomab with historical PET-CT negative results as long as PET-CT was performed \leq 6 weeks from day 1 cycle 1 (first dose of blinatumomab) and subject has no clinical signs or symptoms suggestive of disease progression (eg, increase in LDH not otherwise explained) as described in [Section 4.2.1](#) (Part 2 Inclusion Criteria). Every attempt should be made to complete PET and CT within 3 days of each other.

Pregnancy testing must be completed 72 hours prior to the first dose of blinatumomab.

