10.4.4.3 Laboratory Test Results

Shift tables between the worst post-baseline and baseline grades for selected laboratory parameters will be provided. The analyses of selected safety laboratory parameters including immunoglobulins, platelets, and liver parameters will include summary statistics over time.

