9.6.3 Laboratory Test Results

Summary statistics over scheduled visits for actual values, changes from baseline of laboratory parameters listed below will be presented. In addition, shift tables will be summarized with toxicity grades using CTCAE by worst on-study increase and decrease values between study baseline and any visit up to the end of the study. The schedule of assessments is pre-specified in Table 4 of protocol amendment 3 dated July 18, 2018.

1. Corrected Calcium
2. Magnesium
3. Total bilirubin
4. Direct bilirubin
5. Alkaline phosphatase

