9.6.5 Physical Measurements

Weight will be summarized at pre-specified times during treatment and at the safety follow-up (30 days after treatment). Changes from baseline and percent change will also be calculated. Additionally, summaries of the subject incidence with notable abnormalities defined in [Appendix A, Table 14-2](#) in Full Analysis Set will be presented.

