Appendix A. Reference Values/Toxicity Grades

Safety Laboratory Data

Treatment emergent laboratory abnormalities are defined as those which occur between the start of the first infusion of blinatumomab and the end of the treatment period.

Safety laboratory values below a distinct limit (eg, detection limit, documented as “< [limit]”) will be substituted by half of the limit and values above a distinct limit (documented as “> [limit]”) will be substituted by the limit itself for all analyses.

Grading (based on CTCAE version 4.03 or above) will be assigned to each laboratory result as detailed in [Table 14-1](#). Depending on the toxicity definition, the same result may be assigned to two gradings for deviations towards higher or lower values. In case no lower limit of normal is provided for the absolute lymphocyte, neutrophils or leukocyte counts, it will not be differentiated between grade 1 and grade 0 results for these parameters. Values not meeting any of the criteria will be assigned a grade 0.

Table 14-1. Grading of Selected Laboratory Parameters

Laboratory Parameter [Unit]	Grade 1	Grade 2	Grade 3	Grade 4
Lymphocytes [G/L]	0.8 - < LLN	0.5 - < 0.8	0.2 - < 0.5	< 0.2
Neutrophils [G/L]	1.5 - < LLN	1.0 - < 1.5	0.5 - < 1.0	< 0.5
Leukocytes [G/L]	3.0 - < LLN	2.0 - < 3.0	1.0 - < 2.0	< 1.0
Platelets [G/L]	75 - < LLN	50 - < 75	25 - < 50	< 25
Hemoglobin [g/L]*	100 - < LLN	80 - < 100	65 - < 80	< 65
Albumin [g/L]	30 - < LLN	20 - < 30	< 20	not defined
AST*	> ULN – 3*ULN	> 3*ULN – 5*ULN	> 5*ULN – 20*ULN	> 20*ULN
ALT *	> ULN – 3*ULN	> 3*ULN – 5*ULN	> 5*ULN – 20*ULN	> 20*ULN
GGT	> ULN – 2.5*ULN	>2.5*ULN – 5*ULN	> 5*ULN – 20*ULN	> 20*ULN
Bilirubin	> ULN – 1.5*ULN	>1.5*ULN – 3*ULN	> 3*ULN – 10*ULN	> 10*ULN
Fibrinogen^	%change of BL <25% or 0.75*LLN - < LLN	25%- <50% of BL or < 75*LLN – 0.5*LLN	50% - <75% of BL or < 0.5* LLN – 0.25*LLN	>= 75% of BL or < 50mg/dL or < 0.25*LLN

Page 1 of 2

Footnotes defined on the next page of the table

Table 14-1. Grading of Selected Laboratory Parameters

Laboratory Parameter [Unit]	Grade 1	Grade 2	Grade 3	Grade 4
Corrected Calcium [mmol/L]*	2.0 - < LLN	1.75 - < 2.0	1.5 - < 1.75	< 1.5
Potassium [mmol/L]*	not defined	3.0 - < LLN	2.5 - < 3.0	< 2.5
Lipase	> ULN – 1.5*ULN	> 1.5*ULN – 2.0*ULN	> 2.0*ULN – 5.0*ULN	> 5.0*ULN
Amylase	> ULN – 1.5*ULN	> 1.5*ULN – 2.0*ULN	> 2.0*ULN – 5.0*ULN	> 5.0*ULN

Page 2 of 2

BL: baseline value, LLN: Lower limit of normal, ULN: Upper limit of normal

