*: Clinical criteria from CTC AE 4.0 grading were not considered in order to assign grades

^: In case of conflicting criteria the higher grade will be assigned, % change only used when baseline is <LLN

For more details refer The **Common Terminology Criteria for Adverse Events (CTCAE)**, version 4.03 which is available at the following location:

https://evs.nci.nih.gov/ftp1/CTCAE/CTCAE_4.03_2010-06-14_QuickReference_8.5x11.pdf

Notable values for vital signs are defined according to the following table

Table 14-2. Notable Abnormalities of Vital Signs

Vital Signs	Notable Abnormalities
Pulse rate (bpm)	>120 <50
Blood pressure (mmHg)	Systolic ≥160 ≤90 Diastolic ≥105 ≤50
Weight (kg)	change from baseline ≥10% (in both directions)
Body temperature (°C)	> 39

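### The SAP's fallback baseline rule has no pre-dose condition, so a missed day 1 value can be replaced by an on-treatment one (minor; descriptive safety tables only)

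*SAP*

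**What the plan says.** SAP Section 5 (Definitions, Baseline) gives two rules. For an assessment scheduled on the day of first dosing, baseline "is the last value measured before the first administration of blinatumomab on that day". For an assessment not scheduled that day, or scheduled and not done, "the baseline value is the value measured closest to the day of first administration of blinatumomab". The first rule requires a pre-dose value. The second sets no direction in time and does not say what to do when two values are equally close.

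Baseline feeds these outputs:

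- **Laboratory data.** SAP 9.6.3 plans changes from baseline and states that "shift tables will be summarized with toxicity grades using CTCAE by worst on-study increase and decrease values between study baseline and any visit". Protocol 10.4.4.3 describes the same output: "Shift tables between the worst post-baseline and baseline grades for selected laboratory parameters will be provided".
- **Weight.** SAP 9.6.5 states: "Changes from baseline and percent change will also be calculated". SAP Table 14-2 flags a change of 10% or more in either direction.

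SAP Appendix A separately treats laboratory abnormalities as treatment-emergent when they are "defined as those which occur between the start of the first infusion of blinatumomab and the end of the treatment period".

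No other text in either document adds a pre-dose condition. SAP 8.3 sends the reader to Sections 6 and 10 for missing-data rules, but Section 6 defines analysis sets and Section 10 reports no changes from the protocol.

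**The concern.** The fallback is the SAP's own instruction for a missed day 1 value. Because day 2 is only one day from day 1, the nearest value will often be one taken during the infusion. A programmer following the text would label that value as baseline, and two programmers could resolve a tie differently.

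For an affected subject, laboratory changes, CTCAE shifts and weight changes would be measured from an on-treatment value. A day 2 laboratory result also falls inside the Appendix A window, so the same number could count as both baseline and treatment-emergent. For immunoglobulins, the baseline could follow the whole course of treatment.

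**Working it through.** The plan states no figure that depends on this rule, so there is nothing to reproduce. The check applies the literal rule to the visit schedule.

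**Inputs**

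- Run-in 2 is completed within 7 days of the first dose (Protocol 7.2.3).
- Chemistry, hematology and weight are marked at run-in 2, day 1 and day 2 (Protocol Table 4).
- Immunoglobulins are marked at day 1, day 57 and follow-up, with no screening or run-in sample (Table 4).
- LDH is marked at run-in 2 and not on day 1 or day 2 (Table 4).
- Planned cumulative dose: 7 × 9 + 7 × 28 + 42 × 112 = 4963 µg (SAP Section 5).

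**Which value is closest when day 1 is missed.** Run-in 2 at *k* days before dosing has distance *k*. Day 2 has distance 2 − 1 = 1.

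| Run-in 2, days before dosing | Value selected |
|---|---|
| 0 | a same-day pre-dose value exists; safe |
| 1 | tie (1 versus 1), no rule |
| 2 to 7 | day 2, on treatment |

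Day 2 is selected at 6 of the 8 possible offsets. This counts offsets; it is not a probability.

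**Items reached.** SAP 9.6.3 lists 16 items. Removing LDH and immunoglobulins leaves 14:

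- 10 chemistry: corrected calcium, magnesium, total bilirubin, direct bilirubin, alkaline phosphatase, AST, ALT, amylase, lipase, creatinine.
- 4 hematology: hemoglobin, platelets, neutrophils, lymphocytes.

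Ten of the 14 are graded in SAP Table 14-1: lymphocytes, neutrophils, platelets, hemoglobin, AST, ALT, bilirubin, corrected calcium, lipase and amylase. Weight is reached as well. LDH is not, because run-in 2 is its nearest value.

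**Immunoglobulins.** With no scheduled earlier sample, the first post-dose sample is taken. That is normally day 57, at distance 57 − 1 = 56 days and after all 4963 µg planned, so the day 57 change is zero by construction. If treatment stops early, the safety visit can come first. With the last dose on day *d*, it falls nominally on day *d* + 30, which is before day 57 when *d* ≤ 26. Immunoglobulins have no grades in Table 14-1, so their CTCAE shifts are not at issue.

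**Exposure before a day 2 baseline.** About 9 µg, or 9/4963 = 0.18% of the planned dose. This describes exposure, not the size of any laboratory error.

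**Weight of one subject.** 1/30 = 3.3% of a primary-analysis table.

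**The case against.** The strongest case against is that the fallback is sound in its main use. For an assessment never scheduled on day 1, such as LDH, it correctly picks run-in 2. The problem sits only in the missed-assessment branch, which should be rare because Protocol 7.2.4 requires procedures to be finished before the infusion starts. The contrast between baseline and post-baseline grades, together with the Appendix A window, suggests that a pre-treatment baseline was intended. Grade 3 and 4 laboratory values are recorded as adverse events regardless (Protocol 9.2.2.1), and actual values by visit are still shown.

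Most of this stands, and it limits the importance of the point. It does not repair the rule. Protocol 7.2.4 governs conduct, not derivation, and Protocol 7.2 itself provides for tests not done. Intent inferred from context does not override a sentence that omits the condition stated just before it.

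Two cautions on scope also stand. Vital signs fall under the same wording, and the in-hospital readings every 4 to 8 hours (Protocol 7.3.7) follow initiation, so they do not secure a pre-dose value. If the only day 1 reading is post-dose, neither baseline sentence clearly applies. Second, Table 4 and its copy in the Amendment 3 description of changes differ in some columns as extracted. The run-in 2, day 1, day 2 and day 57 marks used here agree in both. Coagulation does not agree at day 2 and is left out.

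**Conclusion.** The concern holds, as a minor point. Followed literally, the fallback gives an on-treatment baseline for 14 laboratory items and weight when day 1 is missed and run-in 2 was 2 to 7 days earlier. It gives a post-dose immunoglobulin baseline whenever day 1 is missed and no unscheduled pre-dose sample exists.

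The effect is confined to descriptive safety summaries. MRD status at entry is fixed as positive for every treated subject, PFS and OS run from the first dose, and neither DLT stopping nor the adverse event tables use this baseline.

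The conclusion assumes that closeness is measured in calendar days and that visits follow Table 4. The documents do not show how often day 1 values will be missed or which way the error would run, so no count or direction is claimed.

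**What to change.** Replace the fallback sentence in SAP Section 5 with:

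> For assessments not scheduled, or scheduled but not performed, before dosing on day 1, baseline is the last non-missing value measured before the first administration of blinatumomab; if there is none, baseline is missing.

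This removes both the post-dose selection and the tie. It also covers a day 1 assessment made only after the infusion has started.

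The cost is one sentence and no new data. Table 4 already places the full chemistry and hematology panels and weight at run-in 2. Part 2 inclusion criterion 114 independently requires 7 of the 14 items for treatment assignment: neutrophils, hemoglobin, platelets, AST, ALT, total bilirubin and creatinine (through clearance).

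The one downside is that a missed day 1 immunoglobulin baseline stays missing, because no earlier sample is scheduled. That is preferable to reporting a post-treatment value as baseline.
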